### **Design**

This study will recruit 38 healthy participants, who will be recruited through the community via study advertisements. Prior to any study visits, all subjects will be pre-screened through a phone interview with a trained member of the study team or an online self-report screening, both through REDCap. The study involves 11 study visits. The first study visit will consist of a consenting and extended screening visit. All participants will have the opportunity to ask questions before signing the electronic consent form. We will complete a semi-structured clinical interview and will demonstrate TMS to ensure the participant is comfortable with all study procedures. This visit will be completed both remote and in- person. The second study visit will involve a 1-hour MRI scan. During the scan, the participant will complete multiple computerized tasks. The MRI scan will include both structural and functional scans, and those scans will be used to localize the stimulation target for the subsequent sessions. The third study visit will be a 2-hour TMS/fMRI session, and the participant will engage in behavioral tasks while interleaved rTMS rounds are delivered at different excitatory frequencies (frequency range: 2Hz-20Hz). This scan will be used to determine the optimal stimulation frequency for the individual participant. The fourth, fifth, and sixth study visits will involve neuromodulation with either the optimized frequency or the frequency least successful in moving a participants brain state, as determined from the third study visit. Each subject will receive ~3000 pulses in each session, including the pulses from the motor threshold determination. We will determine the adjusted MT by using the Stokes equation, which accounts for differences in cortical distance from the site relative to motor cortex (where the motor threshold is found). The stimulation amplitude will be equivalent to 110% of the adjusted MT. Prior studies have safely utilized TMS with such design (VanDerwerker et al., 2018; Cristancho, Trapp, Siddiqi, Dixon, & Lenze, 2018). The seventh study visit will involve a 1-hour TMS/fMRI session while the participant is engaging in a behavioral task.. This visit is designed to examine brain and behavioral changes after the first round of neuromodulation. The seventh and the eighth visit will be scheduled at least one week apart. The eighth, ninth, and tenth study visits will mirror the fourth, fifth, and sixth study visits and will involve neuromodulation with either the optimized or least-optimized individual frequency. The order of optimized and least-optimized frequencies will be counterbalanced across participants between Visit 4-6 and Visit 8-10 (i.e., half of the participants will receive stimulations of the two frequencies in one order, and the other half will receive stimulations of the two frequencies in the reverse order). The

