## **Characteristics of the Study Population**

#### **Target population**

38 healthy control participants to collect useable data from 28 healthy participants.

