#### **Accrual**

All recruitment will be conducted through the University of Pennsylvania and the surrounding community to find a total of 38 healthy participants. It is assumed that there will be some participants who screen fail, are lost to follow up, withdraw, or complete without usable scanner data. Therefore, we estimate that we will need to consent/enroll up to 38 participants overall, in order to adequately test the hypotheses on at least 28 participants.

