## Procedures

All participants will be recruited through the University of Pennsylvania and the surrounding community. Subjects will be pre-screened for eligibility through phone or online self-report screener in REDCap. Eligible subjects will be invited in for a screening visit. Visit 1 will be a consent/ screening session. This visit will involve remote and in-person procedures. During the remote visit, a coordinator will discuss the Informed Consent Form with the participant. After going through the ICF, participants will be asked to electronically sign at the end of the ICF and complete a Remote ICF Attestation form to ensure they understood all the procedures and risk associated with the study. If they agree to participate, they will complete questionnaires related to their medical history, demographics, and eligibility to receive MRI scans and TMS. After completing the questionnaires, participants will undergo a clinical interview. This interview could be done in person or remote. If participants meet eligibility for these initial procedures, we will schedule an in-person meeting to test TMS. For the TMS demo, participants will receive several short rounds of TMS test pulses to the prefrontal cortex to ensure comfort. During this demonstration we will identify the participants resting motor threshold (MT). MT is defined as the minimum magnetic flux needed to elicit a response in a target muscle in 5 out of 10 trials. MT is the standard in the field for measuring cortical excitability and to reduce seizure risk. While TMS is usually quite tolerable, a minority of participants (20%) cannot tolerate stimulation procedures. Screening data will be recorded in REDCap; this data will be retained indefinitely until the study enrollment is completed. The information collected in this initial visit will determine if the subject meets all inclusion criteria. If participants screen-fail or withdraw, we will assign the clinical interview compensation to their virtual Greenphire Clincard. Upon meeting all criteria for inclusion in the study, subjects will then return to complete a 1-hour baseline MRI scan at Visit 2. All MRI imaging protocols will be reviewed and approved by CAMRIS. An experienced technician and a member of the study team will be present during the MR session to ensure participant safety and well-being. If the participant complains of feeling claustrophobic and does not wish to complete the MRI, the study will be terminated. Emergency personnel and equipment are immediately available to the MRI room should the need arise. It is possible that during the course of the research study, the research staff may notice unexpected findings on an MRI scan. Should this occur, the findings will be assessed by a trained radiologist. The study doctor will inform research subjects of any significant findings. Visit 3 will include fMRI and interleaved TMS/fMRI. During this scan, the participant will perform a working memory N-back task several times. Brain data from the baseline MRI scan (stimulation target in individualized brain space) will be calibrated with the skin and scalp using a Polaris Vicra camera (Brainsight neuronavigation) to allow marking of the stimulation site on a swim cap for the TMS/fMRI session. During the MRI scan, participants will receive interleaved TMS/fMRI probes to the brain targets. The purpose of this TMS/fMRI scan is to probe and modulate and measure activity in targeted neural circuits following our established methods (Chen et al., 2013). Moreover, by building brain decoding models using LSTM RNNs deep-learning technique, we can establish a closed loop of rTMS and brain readouts. As a result, we will be able to fine-tune the rTMS frequency to achieve optimal brain state and maximized working memory performance during this session. Our MRI-compatible TMS system (MagPro X100 Stimulator, MRI-B91 TMS coil) is housed in Stellar Chance (SC3T) and the Hospital of the University of Pennsylvania (HUP 6) at the 3-Tesla MRI machine. The apparatus was installed under the supervision of [name]. a member of CAMRIS. TMS in an MRI scanner involves no additional risks to the subject. Visits 4-6 will involve excitatory rTMS delivered in the

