
same interleaved pattern at the same stimulation site as the TMS/fMRI session but with either the optimized frequency determined from that session or the frequency least successful in moving their brain state (half of the participants will receive optimized stimulation frequency, and the other half of the participants will receive least-optimized stimulation frequency during these sessions). The present study utilizes the same FDA-approved devices (Magventure Cool-Coil B65, MagVenture X100 Stimulator) to administer TMS. The TMS system is housed in the Richards Biomedical Building. Only individuals trained by the Principal Investigator ([name].) and, [name] (M.D.) will dispense TMS. In addition to receiving TMS, participants will complete questionnaires and computerized tasks during these visits. The tasks will assess reaction time, working memory, decision-making. The decision-making task will be incentive-based and the amount the participant earns will be added to their final study compensation. During some of the tasks, we may ask subjects to wear a passive eye-tracking device to record the location of your gaze at any particular time. The order of tasks will be randomized for each participant. Visit 7 will involve a 1-hour TMS/fMRI session. Participants will complete the working memory N-back task while inside the scanner. The purpose of this visit is to examine the brain and behavioral changes after the first round of neuromodulation. Visit 8-10 will mirror Visit 4-6 and will involve neuromodulation with either the optimized or least-optimized individual frequency. The order of optimized and least-optimized frequencies will be counterbalanced across participants between Visit 4-6 and Visit 8-10 (i.e., half of the participants will receive stimulations of the two frequencies in one order, and the other half will receive stimulations of the two frequencies in the reverse order). Visit 7 and the Visit 8 will be scheduled at least one week apart. In addition, unless the MRI is unavailable or we encounter scheduling constraints, Visit #3-Visit #7 will be scheduled within the same work week, such as Visit #3 is on Monday, Visits #4-7 are Tuesday/ Wednesday/Thursday, respectively, and Visit #7 is on Friday. Similarly, Visit #8-Visit #10 will be scheduled 4 work-days in a row, either Monday-Thursday or Tuesday-Friday. Visit 11 will mirror Visit 7 and examine brain and behavioral changes after the second round of neuromodulation. Monitoring will include: (1) successful recruitment, retention; (2) subject adherence; (3) safety and tolerability.

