**Analysis Plan**

For the primary within-subjects analyses, a time (pre vs post rTMS) by condition (optimized vs least-optimized frequency) ANOVA will be done both on task performance as well as fMRI voxelwise brain responses.

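### Where an outcome has its own pre-stimulation value in each round, the planned ANOVA subtracts that value instead of adjusting for it, which multiplies the variance by 2/(1+r)

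*Combined protocol and SAP*

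**What the plan says.** The Analysis Plan is a single sentence: "a time (pre vs post rTMS) by condition (optimized vs least-optimized frequency) ANOVA will be done both on task performance", with the same model used for voxelwise fMRI. It names no baseline covariate and no order or period term, and it does not say which visit supplies the pre value for either condition. The section on primary outcomes defines them as changes in task performance and in brain activity.

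The trial is a two-period crossover: "The order of optimized and least-optimized frequencies will be counterbalanced across participants between Visit 4-6 and Visit 8-10" (Design). According to Study duration, scans take place at Visits 2, 3, 7 and 11 only. Visit 7 follows the first round of stimulation and Visit 11 the second, so no scan falls between Visit 7 and the start of round 2. Outside the scanner, Procedures says of Visits 4-6: "In addition to receiving TMS, participants will complete questionnaires and computerized tasks during these visits". It adds: "Visit 8-10 will mirror Visit 4-6 and will involve neuromodulation with either the optimized or least-optimized individual frequency". It does not say whether the tasks come before or after stimulation, or whether any of them serves as a pre measure.

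The target is "38 healthy control participants to collect useable data from 28 healthy participants" (Target population). Accrual gives the reason for enrolling 38: "in order to adequately test the hypotheses on at least 28 participants". No standard deviation, correlation, effect size, significance level or power accompanies these numbers.

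**The concern.** In a 2x2 within-subject ANOVA the effect of interest is the interaction: the change under the optimized frequency minus the change under the least-optimized one. Because the design is a crossover, stable differences between people cancel before any baseline is used. Subtracting a separate pre value in each round then brings in two more noisy measurements and fixes the coefficient on the pre difference at 1. The best coefficient is r, which is below 1 unless the pre and post differences agree perfectly. A regression estimates that coefficient from the data and so gets more from the same participants.

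The stake is power. The sample is small, and no stated margin would absorb a loss. The planned test could miss a difference that an adjusted analysis of the same data would be likely to find.

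**Working it through.** **The plan's own figures.** The 28 cannot be re-derived, because no power inputs are given. Going from 28 to 38 implies a loss of 10/38 = 26.3%. The one rate stated, 20% unable to tolerate stimulation, would give 28/0.80 = 35. Accrual also lists other causes of loss, so this is not a contradiction, and nothing below depends on it.

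**Case 1: a true pre value in each round.** Let D_pre and D_post be a participant's optimized-minus-least-optimized differences, with equal variance s² and correlation r.

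- Planned interaction, mean of D_post − D_pre: variance 2s²(1−r)/n.
- Adjusted contrast, D_post regressed on D_pre: variance s²(1−r²)/n.
- Ratio: 2(1−r)/[(1−r)(1+r)] = 2/(1+r).

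A numerical check confirmed that the interaction F equals the squared paired t on change scores (2.2189 for both). If values from the same round correlate ρ_w and values from different rounds ρ_b, then r = (ρ_w − ρ_b)/(1 − ρ_b).

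In the table, worth of 28 is 28(1+r)/2. The last two columns give the difference detectable at n = 28 in units of s, for an assumed two-sided 5% level and 80% power (paired standardized effect 0.549), before the cost of estimating the slope.

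| r (assumed) | Variance ratio | Worth of 28 | Detectable, planned | Detectable, adjusted |
|---|---|---|---|---|
| 0 | 2.00 | 14 | 0.777 | 0.549 |
| 0.25 | 1.60 | 17.5 | 0.673 | 0.532 |
| 0.5 | 1.33 | 21 | 0.549 | 0.476 |
| 0.8 | 1.11 | 25.2 | 0.347 | 0.330 |

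Simulation at n = 28, which includes the cost of estimating the slope, gave ratios of 1.96, 1.52, 1.29 and 1.07 at these four values. A second simulation had order in both models and ρ_b assumed at 0.6. Where the adjusted test had about 80% power, the planned interaction had about 51%, 62%, 71% and 77% at ρ_w of 0.6, 0.7, 0.8 and 0.9 (r = 0, 0.25, 0.5 and 0.75).

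**Case 2: one Visit 2 or 3 baseline for both conditions.** D_pre is zero for everyone, the interaction reduces to post minus post, and the ratio is exactly 1.00.

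**Case 3: Visit 7 reused as the pre value for round 2.** With baseline B, the contrast is 2·V7 − B − V11, with the sign reversed in the other order. Take equal correlations ρ among visits and no carryover.

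- Variance: (4+1+1)σ²(1−ρ) = 6σ²(1−ρ), against 2σ²(1−ρ) for post versus post, a ratio of 3.0.
- Expectation: with effects a (optimized) and b (least-optimized), the two orders give 2a − b and a − 2b. Their mean is 1.5(a − b).
- Net precision loss: 3.0/1.5² = 1.33.

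Using Visit 7 as a covariate does not rescue this. The slope is −0.5 and the mean of D_pre is −(a − b)/2, so the intercept is (a − b) − 0.25(a − b) = 0.75(a − b). Simulation confirmed the 0.75. Post versus post with order in the model recovered the whole effect, with 82% power against 68% for the planned test.

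**The case against.** The strongest reply is that a pre value in each round is nowhere established. Visits 7 and 11 are the ones designated to show brain and behavioral change, and round 2 has no scan of its own beforehand. If Visit 2 or 3 is the baseline for both conditions, there is no loss at all. This stands: Case 1 can apply only to the tasks at Visits 4-6 and 8-10, and only if some are done before stimulation.

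The second reply is that r is assumed. This also stands. A reader might infer that the plan throws away half of its 28 participants, but that is the r = 0 end, where measurements from the same round agree no better than those from different rounds. At r = 0.8 the loss is about 3 participants.

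Third, the planned test is valid and answers a question about change, which is how the outcome is defined. In null simulations of Case 1 its type I error was 0.043 to 0.067. The issue is efficiency, except under Case 3, where the estimate is also rescaled.

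A reader might also infer that subtraction favours the hypothesis, because benefit left over at Visit 8 would be charged against the least-optimized round. The arithmetic does not support this as a reason to change. Suppose 0.2 SD carries over from the optimized condition only. Counterbalancing halves it to 0.10 SD. At r = 0.25, if it fades by the post-test, the planned contrast is inflated by 0.10 SD and the adjusted one by 0.025 SD. If it persists, the planned contrast is unbiased and the adjusted one leans 0.075 SD toward the null. The advantage is 0.075 SD either way, and equal carryover from both conditions gives no bias.

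**Conclusion.** The concern holds conditionally. For an outcome with a true pre-stimulation value in each round, the planned interaction has 2/(1+r) times the variance of the adjusted contrast: 2.0 to 1.11 for r assumed between 0 and 0.8, so that 28 participants are worth about 14 to 25. This rests on equal variances of the pre and post differences and on an r that the documents do not supply. With a common Visit 2 or 3 baseline the loss is zero. If Visit 7 stands in as the second pre value, the contrast mixes in the other condition's effect, is rescaled 1.5 times, and loses precision about 1.33 times under equal correlations and no carryover. The documents do not support the stronger reading that every primary outcome is affected. Since the Analysis Plan leaves the pre value undefined, all three cases remain open. This should be settled before analysis.

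**What to change.** In the Analysis Plan, define the pre value for each outcome and state when the tasks at Visits 4-6 and 8-10 are done relative to stimulation. Then:

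- (a) For outcomes with a true pre value in each round, make the primary test a per-participant regression of post(optimized) minus post(least-optimized) on order (+1/−1) and on pre(optimized) minus pre(least-optimized). The intercept is the condition effect.
- (b) For in-scanner outcomes, compare Visit 7 with Visit 11 by condition, with order in the model. Do not use Visit 7 as a pre value or as a covariate.
- (c) Keep the time-by-condition interaction as a sensitivity analysis.

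The cost is one paragraph of wording and, under (a), one error degree of freedom for the baseline slope. No new data are needed. The downside of (a) is a small lean toward the null if unequal carryover persists through round 2 (0.075 SD in the example above). Comparison with the retained interaction would help to show it.

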## **Objectives**

### **Overall objectives**

We aim to evaluate whether optimized frequency (compared to the least-optimized frequency) of excitatory TMS will generate better results in behavior and brain activity among healthy participants. Specifically, we will develop a novel tool to compute individualized multi-scale functional connectivity networks using data from baseline resting and task-evoked brain states. Building on that, we will utilize recurrent neural networks (RNN) with long short-term memory (LSTM), a promising deep learning technique, to generate brain decoding models and obtain real-time readouts of brain states. We will then establish a closed loop of rTMS and brain readouts, fine-tuning the rTMS frequency to determine the optimal stimulation frequency for each participant. Participants will receive their optimal stimulation frequency of rTMS over a three-day neuromodulation session and their least optimal stimulation frequency (the frequency least successful in moving their brain state) over another three-day neuromodulation session (order counterbalanced across subjects). We hypothesize that optimal frequency will drive performance improvements and brain changes more than the least optimal frequency.

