### **Background**

Repetitive TMS (rTMS) has been widely adopted to non-invasively stimulate the brain to improve working memory (WM) performance in both clinical and non-clinical samples (Brunoni & Vanderhasselt, 2014). However, behavioral and symptom responses to TMS remain heterogeneous and the factors governing the strength and direction of rTMS effects across individuals remain largely unknown. Accumulating evidence has demonstrated that TMS efficacy hinges upon the precision of TMS targeting, and individualized functional connectivity networks (FCNs) may help accurately identify TMS targets for individuals (Fox, Buckner, White, Greicius, & Pascual-Leone, 2012; Fox, Liu, & Pascual-Leone, 2013; Weigand et al., 2018) since effects of stimulation are propagated throughout both local and distributed brain networks (Herbsman et al., 2009; Kloppel et al., 2008). The functional brain state varies across individuals and within individuals over time (Bassett, Wymbs, Porter, Mucha, Carlson, & Grafton, 2011; Calhoun, Miller, Pearson, & Adal, 2014; Finn, Scheinost, Finn, Shen, Papademetris, & Constable, 2017), which could substantially alter the impact of TMS. Preliminary research suggests that manipulating brain states during the delivery of repetitive TMS (rTMS) neuromodulation augments the behavioral impact of rTMS (Luber et al., 2017). Through manipulation of brain state with a related behavioral task and using fMRI as the feedback signal, it may be possible to tune rTMS delivery to maximally impact the desired brain states in awake behaving study participants in a highly individualized manner. Therefore, improved efficacy of TMS could be achieved through precise TMS targeting and optimal TMS delivery tailored for individuals and optimized online based on real-time readouts of brain states. FCNs derived from functional MRI have demonstrated promising performance for identification of reproducible individualized targets. However, existing methods are limited in that they typically identify group-level functional connectivity networks (FCNs) and focus on resting state fMRI alone. Our recent work suggests that individualized, sparse, non-negative FCNs provide enhanced ability for characterizing the functional brain of individual subjects (Li, Satterthwaite, & Fan, 2017). Moreover, recent evidence suggests that task fMRI can improve upon within-subject and between-subject estimates of stable brain network representations as compared with resting state fMRI only (Finn, Scheinost, Finn, Shen, Papademetris, & Constable, 2017). Based on these findings, current study will focus on both resting and task-evoked brain states and individualized, multiscale, hierarchical functional neuroanatomy, and we will extend upon our recent published work (Li et al., 2017, 2016; Li, Zhu, & Fan, 2018) using deep matrix decomposition techniques (Trigeorgis, Bousmalis, Zafeiriou, & Schuller, 2014; Zhao, Ding, & Fu, 2017). This strategy will yield a set of individualized FCNs that share similar spatial patterns across subjects at multiple scales with a hierarchical organization,

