
facilitating individualized precise TMS targeting. Another major innovation that will facilitate optimal TMS delivery is the brain decoding for real-time online brain readouts. Recent studies have demonstrated promising brain decoding performance of prediction models built upon functional connectivity measures among FCNs within time windows with a fixed width (Shirer, Ryali, Rykhlevskaia, Menon, & Greicius, 2012; Richiardi, Eryilmaz, Schwartz, Vuilleumier, & Van De Ville, 2011). However, such fixed time windows are not likely optimal over different brain states that change at unpredictable intervals. Meanwhile, recurrent neural networks (RNNs) with long short-term memory (LSTM) (Hochreiter & Schmidhuber, 1997) have achieved remarkable advances in sequence modeling (Lipton, Berkowitz, & Elkan, 2015), and these techniques have been successfully applied to EEG and ECoG data analysis (Glaser, Chowdhury, Perich, Miller, & Kording, 2017; Schwemmer et al., 2018). Our recent study has demonstrated that brain decoding models built upon individualized FCNs using LSTM RNNs accurately decode fine-grained WM tasks and motor tasks in real time (Li & Fan, 2018). Therefore, here we will build brain decoding models to obtain real-time readouts of brain states using LSTM RNNs. Besides TMS targeting, rTMS frequency has clear neurobiological consequences successfully measured in-vivo in non-human animal brains in a landmark study (Allen, Pasley, Duong, & Freeman, 2007). Our team has adopted the interleaved TMS/fMRI technique which will allow stimulation of specific nodes while recording fMRI responses from all other brain regions (Chen et al., 2013; Fonzo et al., 2001; Nahas et al., 2001). Building on this basic strategy and the innovative methodology mentioned above, we can fine-tune the TMS frequency based on real-time feedback of TMS induced effects on the brain. Specifically, we will target FCNs identified by a brain decoding model built using LSTM RNNs, apply short trains of in-scanner rTMS, monitor the resulting brain response with fMRI, and tune TMS delivery accordingly. As a result, we can optimize noninvasive brain stimulation through individualized target and frequency. By comparing behavioral and brain responses with optimized and non-optimized stimulation frequencies, this study will provide us novel insight to variability in response to TMS and will potentially enhance the capabilities of the existing device.

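### The only fMRI test in the Analysis Plan is voxelwise although targets and networks are individual, so it may lose sensitivity by an amount the documents do not let us size

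*Combined protocol and SAP*

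**What the plan says.** The Analysis Plan is one sentence. It sets a time (pre versus post) by condition (optimized versus least-optimized) comparison and says that the "ANOVA will be done both on task performance as well as fMRI voxelwise brain responses". It names no region of interest, target site, individual network or decoder output, and no alpha, voxel threshold, registration or smoothing.

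The rest of the protocol individualizes the intervention:

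- Overall objectives: the study will "compute individualized multi-scale functional connectivity networks using data from baseline resting and task-evoked brain states".
- Background: the aim is that "we can optimize noninvasive brain stimulation through individualized target and frequency", and the fault found with current practice is that "existing methods are limited in that they typically identify group-level functional connectivity networks (FCNs".
- Design, on the Visit 2 scans: "those scans will be used to localize the stimulation target for the subsequent sessions".
- Procedures, Visit 3: "Brain data from the baseline MRI scan (stimulation target in individualized brain space) will be calibrated" for neuronavigation.
- Procedures, Visits 4-6: stimulation follows the "same interleaved pattern at the same stimulation site as the TMS/fMRI session". Visits 8-10 mirror these visits.

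Two outcome sections also bear on the point. The primary outcome section names in-scanner brain readouts, during the task or at rest. The secondary outcome section names a correlation between behavioral change and network connectivity change. The Analysis Plan gives no method for either.

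**The concern.** A group voxelwise ANOVA treats a given voxel as playing the same role in every participant. The protocol's own premise is that target and networks vary between people. Where they vary in location, a voxel can lie inside the stimulated network for some participants and outside it for others. The mean condition effect at that voxel then shrinks and its between-person variance rises.

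At stake is how a null map could be interpreted. If the voxelwise map is the only imaging test and it shows nothing, the study could not tell whether frequency made no difference in the brain or whether real effects failed to line up across brains. The protocol states no other imaging analysis that would separate the two.

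**Working it through.** **The plan's own figure.** There is none to reproduce. The Accrual section gives 38 enrolled for at least 28 analyzable (implied loss 1 - 28/38 = 26.3%), with no effect size, alpha or power. I therefore take n = 28 from the protocol and assume the rest.

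**Reduction to one test.** With two times and two conditions within person, the interaction is a one-sample t-test on each person's difference of differences, with 27 degrees of freedom. Power comes from the noncentral t with noncentrality dz × √28. At two-sided 5%, 80% power at the person's own site needs dz = 0.549 (0.549 × 5.292 = 2.91).

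**Overlap model.** Let a share p of participants have the voxel inside their own stimulated network with effect d (SD 1), and let the others carry h × d. Then

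- mean = d × [p + h(1 - p)]
- SD = √(1 + d²(1 - h)² p(1 - p))
- effective dz = mean / SD

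Example, p = 0.5:

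- h = 0: mean 0.275, SD 1.037, dz 0.265, power 27%.
- h = 0.5: mean 0.412, SD 1.009, dz 0.408, power 55%.

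| Overlap p | Power, h = 0 | Power, h = 0.5 |
|---|---|---|
| 100% | 80% | 80% |
| 90% | 70% | 76% |
| 70% | 48% | 66% |
| 50% | 27% | 55% |
| 30% | 13% | 44% |

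**Second model, as a check.** Treat each person's effect as a Gaussian of width FWHM on a two-dimensional cortical sheet, with targets scattered by SD s per axis. With σ = FWHM/2.355, mean attenuation is σ²/(σ² + s²), and the between-person variance of the attenuation is added to the error. For FWHM 15 mm and s = 5 mm: σ² = 40.6, attenuation 40.6/65.6 = 0.62, power 40%.

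| FWHM | s = 2 mm | s = 5 mm | s = 8 mm | s = 10 mm |
|---|---|---|---|---|
| 10 mm | 63% | 21% | 9% | 7% |
| 15 mm | 72% | 40% | 19% | 13% |
| 20 mm | 76% | 54% | 31% | 21% |

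These are powers at the best-placed group voxel, two-sided 5%, against 80% at the person's own site. Every overlap share, partial effect, width and scatter value is an assumption.

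**Why I use one alpha.** The plan states no voxel threshold. A stricter one such as p < 0.001 would also not compare the plan with the remedy, because a single value per person would not be tested at that level. The effect that gives 80% power at 0.001 (dz = 0.869) already has 99% power at 5%. That gain comes from making fewer tests and has nothing to do with alignment.

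**The case against.** The strongest reply is that the loss may be small, and the Background section supports it in two ways. It says the individualized networks will have similar spatial layouts across participants, so they are built to correspond. It also says stimulation effects spread through local and distributed networks, so a participant whose target lies elsewhere need not show zero effect at a given voxel. The half-effect column and the 2 mm scatter column show how far this can soften the result: 76% at 90% overlap, and 72-76% for widths of 15-20 mm. This stands, and it rules out any statement that power is certain to be lost. It does not remove the point. Similar networks need not coincide, and individualizing them would serve little purpose if they did.

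A second reply is that the declared primary brain outcome is the readout, and the decoding models are to be built on individualized networks. Testing that readout would largely answer the concern. That is fair, but the Analysis Plan does not test it, and the connectivity outcome has no method either.

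A reader might also infer that misalignment distorts the comparison between frequencies. The documents do not support this. Each person is stimulated at the same site under both conditions, so the mismatch is between people and not between conditions.

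**Conclusion.** The point holds as a limited one. The only fMRI test specified in the Analysis Plan is voxelwise, and no stated analysis looks at each person's own target or network. To the extent that targets and networks differ in location between people, sensitivity may be lost; the contrast itself stays valid.

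The loss cannot be sized from the documents. Under the assumptions above, power could fall from 80% to anywhere between 76% and 13% for overlaps of 90% down to 30%, depending also on how much effect non-overlapping participants carry. The reading rests on the voxelwise ANOVA being run in a common space, which is usual but not stated. Two stronger conclusions go beyond the text: that each person's effect will in fact be averaged with unstimulated tissue, and that the voxelwise result will be a false null.

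**What to change.** In the Analysis Plan, add as the lead fMRI test a time by condition comparison on one pre-specified value per participant and visit, taken in that participant's own individualized target network. Name one region only, delineate it from the Visit 2 data, and fix it before Visit 4. State how this value relates to the in-scanner brain readout in the primary outcome section, so that the outcome and its test are the same quantity.

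Keep the voxelwise ANOVA as a secondary map for distributed effects, and state its registration, smoothing and multiplicity correction.

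The cost is analysis wording and extraction from networks the study already computes for targeting; no scans, visits or participants are added. The small downside is that effects outside the individual network are seen only in the secondary map.
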